Study Protocol

Official

Title:

Evaluation of the Effect of the Mediterranean Diet on Disease Activity and Treatment Response in Patients With Axial Spondyloarthritis Receiving Biologic Therapy

Protocol Number: AS01

Sponsor/Institution:

Erciyes University, Faculty of Medicine, Department of Physical Medicine and Rehabilitation, Division of Rheumatology

Principal

Investigator:

Assoc. [name]

Date:

24 January 2025

Aim

This study aims to investigate the effects of the Mediterranean diet on disease activity, quality of life, inflammation levels, pain scores, and the frequency of biologic DMARD (bDMARD) use in patients with ankylosing spondylitis (AS) receiving biologic therapy.

Potential Risks

There are no anticipated risks associated with this study.

Background

Ankylosing spondylitis (AS) is a chronic inflammatory disease of unknown etiology that typically begins with inflammation in the sacroiliac joints in the early stages and later affects the axial spine.¹ It can lead to significant reductions in quality of life due to inflammatory back pain, structural, and functional impairments. Genetic factors, gut microbiota, mechanical effects on the spine and peripheral joints, innate immunity, oxidative stress, lifestyle, and environmental factors are thought to play an important role in AS pathogenesis.² Accordingly, diet has increasingly been investigated as a potential factor influencing the pathogenesis and progression of AS.

Both pharmacological and non-pharmacological approaches should be used in AS management.³ The main goals of treatment are to control symptoms and inflammation, prevent

structural damage progression, and maximize quality of life.⁴ However, there is limited evidence supporting the impact of lifestyle modifications. Among environmental factors, diet stands out as a modifiable factor with potential to reduce inflammation.⁵ Inflammation can alter metabolism, potentially modifying dietary habits and directly influencing disease activity.⁶ While some foods may trigger inflammatory processes, nutrients such as antioxidants and omega-3 fatty acids demonstrate anti-inflammatory properties.

A study on axial spondyloarthritis (axSpA) patients suggested that diet could have beneficial effects; however, this study also included axSpA patients beyond AS.⁷ Diets rich in fiber and antioxidants may provide protective effects in gastrointestinal and inflammatory processes.⁸

The Mediterranean diet (MD), with its anti-inflammatory and antioxidant potential, is thought to delay the onset and progression of chronic inflammation.⁹ This diet has also been linked to the prevention and management of cardiovascular diseases.¹⁰ The MD includes high intake of olive oil, unrefined carbohydrates, fresh and dried fruits, vegetables, and fish; low intake of dairy products and red meat; and moderate consumption of red wine. It is particularly rich in antioxidants and polyunsaturated fats.

In AS, these nutritional components may reduce inflammation, pain, and structural damage, and potentially lower disease prevalence.⁷ However, to date, no study has compared the effects of the Mediterranean diet in AS patients receiving bDMARDs with a control group. Therefore, our study aims to evaluate the efficacy of the Mediterranean diet in this patient group, contributing to disease management and supporting a therapeutic approach that improves quality of life.

Hypothesis:

The Mediterranean diet will reduce disease activity, improve quality of life, and decrease inflammation in AS patients.

Methods

Study Design and Participants

This is a prospective, single-blind, randomized controlled trial.

Sample size calculation determined that 51 participants per group were required. With an additional 10% dropout allowance, the total target enrollment is 55 participants per group (110 total). Eligible participants will be adults over 18 years old, diagnosed with AS according to ASAS criteria, and providing written informed consent.

Inclusion Criteria:

1. Diagnosis of AS according to ASAS criteria
2. Age \geq 18 years
3. No recent dietary changes in the past 3 months
4. Stable treatment with NSAIDs or DMARDs in the past 4 months
5. Voluntary participation with signed informed consent

Exclusion Criteria:

1. Pregnancy or breastfeeding
2. Dietary restrictions preventing adherence to the Mediterranean diet (e.g., severe food allergies)
3. Participation in another diet or exercise-based intervention within the past 6 months
4. History of another rheumatologic or neurological disorder

Randomization

Participants will be randomized into intervention and control groups using stratified randomization by age, body mass index, and disease activity (ASDAS-CRP). Randomization will be conducted through <https://www.randomizer.org/> by an independent researcher not involved in the study.

Outcome assessors will be blinded to group allocation. The physiotherapist implementing the intervention will not be blinded, but will not participate in outcome assessments.

Interventions

- **Control Group (Standard Care):** Patients will continue their standard medical treatment and receive general healthy nutrition recommendations.
- **Mediterranean Diet Group:** Patients will follow a Mediterranean diet plan supervised by a dietitian. Compliance will be monitored via phone calls every 10 days.

Assessments will be performed at baseline and at 3 months.

Outcomes

Primary Outcome Measure:

- Change in Ankylosing Spondylitis Disease Activity Score with C-reactive protein (ASDAS-CRP) from baseline to 3 months.¹³

Secondary Outcome Measures:

- Bath Ankylosing Spondylitis Disease Activity Index (BASDAI)^{11 12}
- Bath Ankylosing Spondylitis Functional Index (BASFI)
- Bath Ankylosing Spondylitis Metrology Index (BASMI)
- Hospital Anxiety and Depression Scale (HADS)^{14 15}
- Short Form-36 (SF-36)¹⁶
- International Physical Activity Questionnaire (IPAQ)¹⁷
- Pittsburgh Sleep Quality Index (PSQI)¹⁸
- FACIT-Fatigue Scale¹⁹
- Health Assessment Questionnaire (HAQ)²⁰
- Morisky Medication Adherence Scale-8 (MMAS-8)^{21 22}
- PREDIMED Mediterranean Diet Adherence Questionnaire^{23 24}
- Handgrip strength (Jamar Hydraulic Hand Dynamometer)
- Body composition (InBody270 Analyzer)

Statistical Analysis

Sample size was calculated using **G*Power version 3.1.9.7** with 80% power and a 5% type I error, yielding 51 participants per group. With a 10% dropout rate, 55 participants per group will be recruited.

All analyses will be conducted using **SPSS version 22.0**. Normality will be tested with Shapiro-Wilk. Baseline group comparisons will be done using independent t-tests or Mann-Whitney U tests. Repeated measures will be analyzed with mixed-model ANOVA, with Bonferroni correction for multiple comparisons. Categorical variables will be analyzed using Chi-square or Fisher's exact tests. A p-value <0.05 will be considered statistically significant.

References

1. van der Linden S, van der Heijde D. Ankylosing spondylitis: clinical features. *Rheumatic Disease Clinics of North America*. 1998;24(4):663-676.

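### Enrolling 55 per group does not provide the stated 10% dropout allowance: 10% loss leaves 49 to 50 completers per group, below the 51 required

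*Protocol*

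**What the plan says.** The sample size appears twice in the protocol, with the same three figures.

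- Methods, Study Design and Participants: "Sample size calculation determined that 51 participants per group were required". The next sentence reads "With an additional 10% dropout allowance, the total target enrollment is 55 participants per group (110 total".
- Statistical Analysis: the calculation was run in G*Power "with 80% power and a 5% type I error, yielding 51 participants per group", followed by "With a 10% dropout rate, 55 participants per group will be recruited".

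Neither section shows how 51 becomes 55. The protocol gives no effect size, standard deviation or sidedness for the calculation, and nothing elsewhere in it offsets the gap. Because the figures agree in both sections, a slip in a single sentence is unlikely.

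**The concern.** The three figures (51 needed, 10% lost, 55 enrolled) cannot all be right. The purpose of a dropout allowance is that the required number should still be expected to finish after the planned loss. Here the expected number of completers is below the required number. The primary outcome is change in ASDAS-CRP from baseline to 3 months, and the only assessments are at those two times. A participant who drops out therefore has no later measurement to contribute. If dropout occurs exactly as planned, the trial ends below its own required size and its stated power. Any reader can find the inconsistency in one line of arithmetic, which weakens the sample size statement whatever its practical effect.

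**Working it through.** **Inputs from the protocol.** Required number per group 51; dropout 10%; enrolment 55 per group, 110 in total; power 80%; type I error 5%. Equal allocation is implied by the equal group sizes.

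**Step 1. Try to reproduce 55.**

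| Convention | Per group | On the total |
|---|---|---|
| Divide by the retained fraction, N/(1 − d) | 51/0.90 = 56.7, so 57 (114 in total) | 102/0.90 = 113.3, so 114 |
| Add the percentage, N × (1 + d) | 51 × 1.10 = 56.1, so 56 or 57 (112 or 114 in total) | 102 × 1.10 = 112.2, so 112 or 113 |

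Neither convention gives 55 or 110, whether rounded up, down or to nearest. A start of 50 would give 50 × 1.10 = 55, which may be where the figure came from, but the protocol does not say so and states 51 in both places.

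**Step 2. What 55 does cover.**

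- Largest loss that still leaves 51: (55 − 51)/55 = 4/55 = 7.3%.
- Addition relative to 51: 4/51 = 7.8%.

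**Step 3. Completers at the planned 10% loss.**

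- Per group: 55 × 0.90 = 49.5, that is 49 or 50.
- In total: 110 × 0.90 = 99, against 2 × 51 = 102 required.
- With 57 per group: 57 × 0.90 = 51.3, which meets the requirement.

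**Step 4. Effect on power.** The protocol gives no effect size, so this step rests on an assumption. I took a two-sample t-test at the 5% level and solved for the standardised difference that gives exactly 80% power with 51 per group, then recomputed power at the smaller sizes.

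| Completers per group | Two-sided (d = 0.560) | One-sided (d = 0.496) |
|---|---|---|
| 51 | 80.0% | 80.0% |
| 50 | 79.2% | 79.3% |
| 49.5 | 78.8% | 78.9% |
| 49 | 78.4% | 78.6% |

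A normal approximation gives the same values to within 0.1 percentage point.

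Since 51 is a rounded integer, power at 51 may be slightly above 80%. As an illustration, an assumed d of 0.5, one-sided, gives 80.6% at 51, 79.9% at 50 and 79.2% at 49. Power at 49 to 50 completers stays below 80% there too.

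**The case against.** The strongest objection is about size. In Study Design and Participants, an additional allowance of 10% can fairly be read as adding 10% to 51, which gives 56.1. On that reading, rounded to nearest, the target is short by 1 per group (2 in total), not 2 per group (4 in total). Only the Statistical Analysis section, which speaks of a dropout rate, points clearly to 57. The cost is then 1 to 2 percentage points of power, and no design decision turns on that.

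This stands as a limit on the point. The shortfall should be given as 2 to 4 patients in total, depending on the convention. It does not remove the error, because 55 is wrong under the lenient reading as well.

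A second objection is that the power figures depend on a test and an effect size that the protocol does not state, and that the protocol names a mixed-model ANOVA for the repeated measures. That is true, and the figures should be read as approximate. The result barely changes with sidedness, and the shortfall in completers does not depend on these assumptions.

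It would also be unfair to judge 55 by the probability that both groups reach 51. With independent 10% dropout, that probability is 0.345² = 12% at 55 per group, but only 0.657² = 43% at 57. A dropout allowance conventionally aims at the expected number of completers, and 55 fails that standard without any appeal to the 12%.

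**Conclusion.** The point holds. The enrolment target does not follow from the protocol's own required number and dropout figure under either usual convention. It is 1 to 2 per group too low (2 to 4 in total; 4 if 10% is a dropout rate), it covers 7.3% loss instead of 10%, and at 10% it leaves an expected 99 completers against 102. These results use only figures in the protocol.

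The loss of power is small, to roughly 78 to 79%, assuming a t-test with the effect size worked back from 51 per group at 80% power. Whether 51 itself is right cannot be checked, because its inputs are not given. The statement should be corrected, but the error does not endanger the trial.

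**What to change.** Correct the sentence in both Study Design and Participants and Statistical Analysis, choosing one of these:

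1. Keep 55 per group and state that this allows for about 7% dropout (4 of 55).
2. Keep 55 per group and 10% dropout, and state that 49 to 50 completers per group are expected, with about 78 to 79% power. Give the test and effect size behind that figure.
3. Keep 10% dropout and 80% power, and raise the target to 57 per group (114 in total).

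If the calculation actually gave a number other than 51, correct that number first and redo the inflation from it.

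Options 1 and 2 cost two edited sentences and a slightly less favourable dropout or power figure, with no extra enrolment. Option 3 costs four more patients.

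### Does the blinding rule bar the wrong person, by naming a physiotherapist when the diet is supervised by a dietitian?

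*Protocol*

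**What the plan says.** Under Study Design and Participants the protocol states: "This is a prospective, single-blind, randomized controlled trial". The blinding text, which closes the Randomization section, has two sentences. The first is general: "Outcome assessors will be blinded to group allocation". The second concerns one role: "The physiotherapist implementing the intervention will not be blinded, but will not participate in outcome assessments".

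The Interventions section then describes the two arms. For the diet arm: "Patients will follow a Mediterranean diet plan supervised by a dietitian", and "Compliance will be monitored via phone calls every 10 days". The person who makes those calls is not named. For the control arm: "Patients will continue their standard medical treatment and receive general healthy nutrition recommendations". Neither arm contains physiotherapy or exercise, and the protocol mentions a physiotherapist nowhere else. The Outcomes section lists ASDAS-CRP as primary and 13 secondary measures, and does not say who collects any of them.

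**The concern.** Participants know whether they have been given a supervised diet plan, so the blinding that this protocol describes lies with the assessors. It depends on keeping those who know the allocation away from those who measure outcomes. The one sentence that sets this separation by role names a physiotherapist, while the professional tied to the intervention is a dietitian.

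Taken alone, that sentence leaves the dietitian free to assess. Two of the secondary outcomes, the PREDIMED adherence questionnaire and body composition on the InBody270, are measures a dietitian might well collect. BASMI and handgrip strength also depend on whoever takes the measurement. If a person who knows the allocation and is invested in the diet recorded such outcomes, the differences between arms could be biased, plausibly in favour of the diet.

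There is a second worry: a physiotherapist, a natural choice to measure BASMI or grip strength, seems to be ruled out as an assessor.

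**Working it through.** The protocol gives no figure for this point, so the check is a comparison of its sentences.

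**1. Is there a mismatch?** Yes. The blinding text has a physiotherapist implementing the intervention; the Interventions section has a dietitian supervising it. The two roles are not strictly incompatible, because one person can carry out a plan under another's supervision. But no such task is described for a physiotherapist, so the roles are left unreconciled.

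**2. Does the mismatch let the dietitian assess outcomes?** Read the two blinding sentences together.

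| Sentence | Whom it covers | Effect on the dietitian |
|---|---|---|
| General rule ("Outcome assessors will be blinded to group allocation") | every outcome assessor, without exception | the dietitian knows the allocation, so cannot be a blinded assessor and is excluded |
| Role-specific rule | the implementing physiotherapist only | silent; grants no permission |

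The second sentence adds an explicit bar for one role. It does not narrow the first. The same reasoning excludes the caller once that person knows the allocation, which someone checking adherence to the diet would.

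**3. Is any outcome shown to be exposed?** The Outcomes section lists 13 secondary measures: BASDAI, BASFI, BASMI, HADS, SF-36, IPAQ, PSQI, FACIT-Fatigue, HAQ, MMAS-8, PREDIMED, handgrip strength and body composition. None is assigned to a dietitian. The number shown by the text to be exposed is therefore 0 of 13, and nothing ties the primary outcome to the dietitian either. That PREDIMED and body composition would fall to a dietitian is an inference about clinic habits.

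**4. Does the number of calls add anything?** Taking 3 months as about 90 days, 90 / 10 = about 9 calls per diet participant. That measures contact with the intervention team and does not bear on who assesses outcomes.

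**5. Are physiotherapists lost as assessors?** No. The bar applies to the physiotherapist who implements the intervention. Another physiotherapist who is blind to allocation may measure BASMI or grip strength.

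**6. What would rewording alter?** Extending the explicit bar to the dietitian and the caller would exclude people whom the general rule already excludes. The set of permitted assessors would be the same before and after.

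**The case for a change.** The best argument for a change is that the authors added a role-specific bar to the general rule, presumably because they wanted the separation spelled out, and then attached it to a role the protocol does not otherwise use. Staff allocating duties have no sentence saying in so many words that the dietitian and the caller must not assess. Who delivers an intervention is also a matter for the protocol and cannot be put off to an analysis plan. The correction would take one sentence.

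Some of this stands. The label is unreconciled, and naming the caller would make the text clearer. Reading the physiotherapist as someone who carries out the plan under supervision does not fully rescue it either, because the dietitian would still lie outside the explicit bar.

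It does not show that blinding fails. To put the dietitian in an assessor's role, staff would have to breach a plain rule in the sentence just before. For self-completed questionnaires the point has little force in any case: participants know their diet, so their answers are open to that influence whoever hands out the form. The measures with most to lose are those taken by an assessor, such as BASMI and grip strength, and the general rule covers these.

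**Conclusion.** The two sections name different professionals, and that is a slip. It calls for no change to the plan. Followed as written, the protocol has every outcome assessed by someone blinded to allocation, which already keeps out the dietitian and any caller who knows the arm. No outcome is shown to be exposed, and no estimate, sample size or test is affected. Tidying the role label at a convenient moment would do no harm, but it would restate an existing rule.

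This rests on two assumptions. The first is that the general assessor rule is applied without exception, as its wording requires. The second is that the dietitian and caller do know the allocation, which follows from supervising the diet plan and checking compliance with it. Had the protocol assigned a named outcome to the dietitian, the two passages would truly conflict and the conclusion would differ. It does not.

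### Recruiting 55 per group does not cover the stated 10% dropout: it leaves 49.5 per group, below the 51 the protocol says it needs

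*Protocol*

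**What the plan says.** The sample size is given twice. Under Study Design and Participants: "Sample size calculation determined that 51 participants per group were required". A 10% allowance for dropout is then added, giving a target of 55 per group and 110 in total. The Statistical Analysis section names the software and repeats the result, "with 80% power and a 5% type I error, yielding 51 participants per group", followed by "With a 10% dropout rate, 55 participants per group will be recruited".

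Neither place gives the effect size, its SD, the test or the number of tails. The planned analysis is described as follows: "Repeated measures will be analyzed with mixed-model ANOVA, with Bonferroni correction for multiple comparisons". The significance rule is "A p-value <0.05 will be considered statistically significant".

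**The concern.** An allowance for dropout is meant to leave the required number of completers once the expected loss has occurred. Here the required number (51), the expected loss (10%) and the recruitment target (55) are all stated, and the third does not follow from the first two. If dropout runs exactly as the protocol expects, the trial ends with fewer analysable patients than its own calculation requires, and the 80% power it reports is not met.

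The protocol fixes the recruitment target, so a separate statistical analysis plan would not repair this. At stake is the accuracy of the stated power, by a small amount, and the consistency of a figure that will be carried into the trial report.

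**Working it through.** **Inputs from the protocol.** Required completers: 51 per group. Dropout: 10%. Recruitment: 55 per group, 110 in total. Power 80%, type I error 5%.

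**The plan's own figure.** 51 cannot be reproduced from the protocol, because alpha, power and 1:1 allocation do not determine a sample size without an effect size and a test. It is taken as given for the dropout check, which does not depend on how it was derived.

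**Dropout step.**

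- Completers left = recruited × (1 − dropout) = 55 × 0.90 = 49.5 per group. This is 1.5 below 51.
- Recruitment needed = required / (1 − dropout) = 51/0.90 = 56.7, so 57 per group and 2 × 57 = 114 in total.
- The cruder rule of adding 10% gives 51 × 1.10 = 56.1, which also exceeds 55.
- Loss that 55 can absorb = 1 − 51/55 = 7.3%.

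Neither common way of inflating for dropout turns 51 and 10% into 55.

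**Effect on power.** Assume that 51 per group is the number that just gives 80% power on a two-sided two-sample t-test at 5%. The noncentral t distribution then gives a standardised difference of d = 0.560. At that d:

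| Completers per group | Power |
|---|---|
| 51 | 80.0% |
| 50 | 79.2% |
| 49 | 78.4% |

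The loss is therefore about one to two percentage points.

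**Secondary check on the 51.** Several sets of inputs return 51 per group at 80% power:

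- one-tailed t-test, d = 0.5: n = 50.15, rounded up to 51 (power 80.6%);
- two-sided t-test, d of about 0.561 to 0.565;
- two-sided Mann-Whitney test, d of about 0.575 or 0.605, with asymptotic relative efficiency taken as 0.955 or 0.864;
- repeated-measures ANOVA (two groups, two times), f = 0.20 and zero correlation between the two times: N = 102, which is 51 per group.

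Under the first set alone, the calculation would not match the planned F test, which is non-directional. A two-sided t-test at d = 0.5 needs 63.8, so 64 per group, and has 70.6% power at 51 per group. Here d is in SDs of the outcome actually tested.

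**The case against.** **The shortfall is trivial.** It is two recruits per group (57 against 55) and one to two points of power, and actual dropout may be below 10%. That is a fair description of its size and a good reason not to enlarge the trial for it. It does not make the statement correct: the three numbers are the protocol's own and cannot all hold.

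**The tempting stronger reading.** A reader might infer that the calculation was one-tailed at a medium effect, so that the true power is about 70%. Three things point that way. The match at d = 0.5 is exact, that is a conventional value, and the hypothesis is worded in one direction: "The Mediterranean diet will reduce disease activity, improve quality of life, and decrease inflammation in AS patients". The alternatives look less natural: a two-sided t-test needs d within a narrow band near 0.56, and the ANOVA route needs zero correlation between two measurements of the same patient.

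The protocol does not support this as a finding. It mentions neither d = 0.5 nor a one-tailed test. A d near 0.56 could simply come from entering means and SDs from earlier data, and then there is no mismatch. Trials tested two-sided often word their hypothesis directionally. Even granting d = 0.5, the 70% holds only if d is in SDs of the tested outcome; for change in ASDAS-CRP with d in SDs of the score itself, power would depend on the correlation between baseline and 3 months, which is not given. The missing inputs may also stand in a statistical analysis plan that was not available. What remains is a question to the sponsor.

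**Conclusion.** The dropout step is wrong as written, and this needs no assumption beyond the protocol's own numbers: 55 per group less 10% is 49.5, below 51, and 55 covers a loss of about 7.3%. The effect is minor. Power would be about 78% to 79% instead of 80%, on the assumption that 51 is the number that just reaches 80% on a two-sided t-test.

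Whether the 51 itself came from a one-tailed calculation cannot be settled from the protocol. The figure of about 70% is conditional on that reading and should not be reported as the trial's power.

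**What to change.** Correct the dropout sentence under both Study Design and Participants and Statistical Analysis, keeping recruitment at 55 per group. Either of these would do:

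- state that 55 per group with 10% dropout leaves about 49 to 50 completers per group, with power slightly under 80%; or
- state that 55 per group allows for a loss of about 7%.

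If the sponsor prefers to keep both the 10% and the 51, the target becomes 57 per group (114 in total), which is four more patients.

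In the same edit, state the effect size, SD, test and number of tails behind the 51, and confirm that the calculation was two-sided to agree with the ANOVA F test. If it proves to have been one-tailed at d = 0.5, restate the power at 51 per group as about 70% for d = 0.5 in SDs of the tested outcome, or as 80% for d of about 0.56.

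The cost is a reworded sentence in two places and a look at the saved calculation. The stated power becomes slightly less favourable, or clearly less so if the one-tailed input is confirmed. Restating the figures requires no extra enrolment.

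### The primary change in ASDAS-CRP is left to a two-visit mixed ANOVA with no covariates; ANCOVA on baseline and the stratifiers would give more power from the same data

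*Protocol*

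**What the plan says.** Under Outcomes, the primary measure is "Change in Ankylosing Spondylitis Disease Activity Score with C-reactive protein (ASDAS-CRP) from baseline to 3 months". The Interventions section gives the schedule: "Assessments will be performed at baseline and at 3 months". There are therefore two groups and two measurements per patient.

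Under Statistical Analysis, the t-test and Mann-Whitney sentence is confined to baseline comparisons, and the chi-square and Fisher sentence to categorical variables. What remains for a continuous outcome measured twice is: "Repeated measures will be analyzed with mixed-model ANOVA, with Bonferroni correction for multiple comparisons". The protocol names no covariate and does not say which ANOVA term is the primary test.

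The Randomization section specifies "stratified randomization by age, body mass index, and disease activity (ASDAS-CRP"), so baseline ASDAS-CRP, age and BMI must all be known before allocation. The sample size was calculated "with 80% power and a 5% type I error, yielding 51 participants per group".

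**The concern.** The natural test of treatment effect in a two-by-two mixed ANOVA is the group-by-time interaction, and that is a t-test on change scores. Subtracting baseline uses the baseline value with its slope fixed at 1. When the true slope is below 1, this over-corrects and leaves avoidable noise in the comparison.

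Stratification adds to the problem. If allocation is balanced within strata of baseline ASDAS-CRP, the treatment estimate varies less than the unadjusted standard error implies, so the test becomes conservative.

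Neither effect biases the estimate. What is at stake is power and confidence-interval width for the primary outcome, in a trial sized for only 80% power.

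**Working it through.** **Inputs from the protocol.** 51 per group, 80% power, 5% type I error, two visits, three stratifiers. It does not give r (the correlation between baseline and 3-month ASDAS-CRP), the SD, the effect size, sidedness, stratum cut points or block size.

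**The plan's own figure.** 51 per group cannot be reproduced, because no effect size is stated. It fits a one-sided t-test at d = 0.50 (n = 51) or a two-sided t-test at d of about 0.56. A two-sided test at d = 0.50 would need 64 per group, and 51 would give 70.6% power.

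**The identity.** On one simulated data set with 51 per group, the group-by-time F was 1.69088 and the squared t on change scores was 1.69088, both with p = 0.19647.

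**Variance.** With a common SD s at both visits:

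- change score: 2s²(1 − r)
- ANCOVA on baseline: s²(1 − r²)
- ratio of ANCOVA to change score: (1 − r²) / [2(1 − r)] = (1 + r)/2

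**Power.** Assume the change test has exactly 80% two-sided power at 51 per group. The noncentral t with 100 df then gives d = 0.5602 in change-SD units. For ANCOVA, replace d by d/√[(1 + r)/2] and use 97 df (group plus three covariates):

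| r | variance ratio | 95% CI width ratio | ANCOVA power |
|---|---|---|---|
| 0.3 | 0.65 | 0.806 | 93.5% |
| 0.5 | 0.75 | 0.866 | 89.9% |
| 0.7 | 0.85 | 0.922 | 85.9% |
| 0.9 | 0.95 | 0.975 | 82.0% |

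The interval is therefore about 19%, 13%, 8% and 2.5% narrower. If the change test really has 60%, 70% or 90% power, ANCOVA at r = 0.5 has 72.4%, 81.8% or 96.3%. Going from 100 to 97 df costs less than 0.1 percentage points of power.

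**Effect of stratification.** This was simulated with 102 patients and 20,000 runs per cell. The assumptions were median splits on all three factors (8 strata), permuted blocks of 4, and age and BMI without prognostic value:

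| r | type I error, change v ANCOVA | power, change v ANCOVA |
|---|---|---|
| 0.3 | 3.0% v 5.0% | 82.6% v 93.0% |
| 0.5 | 3.3% v 5.0% | 81.7% v 89.4% |
| 0.7 | 3.9% v 5.0% | 81.2% v 85.8% |
| 0.9 | 4.9% v 5.0% | 80.1% v 81.1% |

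The Monte Carlo standard error is about 0.15 points for type I error and 0.3 for power. The gains in power are 10.4, 7.7, 4.6 and 1.0 points. Both estimators were unbiased (mean error at most 0.001 SD).

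**Unequal SDs.** If the 3-month SD is k times the baseline SD, the variance ratio is k²(1 − r²) / (1 + k² − 2rk). At k = 1.2 and r = 0.7 this is 1.44 × 0.51 / 0.76 = 0.966, and ANCOVA power is 81.3%. At r = 0.8 it is 1.44 × 0.36 / 0.52 = 0.997, and power is 80.1%. The ratio never exceeds 1, and it reaches 1 only where the true slope rk equals 1.

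**The case against.** The planned test is valid and widely used, and the calculation above starts by granting it the 80% power the protocol aims for. On that reading nothing falls short of target; extra power is simply not taken. Covariates are also often left to an SAP, and one may exist. The validity point stands, and it is why this is advice on efficiency rather than a correction of error. The SAP point is weaker: the protocol does name a method, and the advice is to replace that method, not to fill a silence.

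The size of the gain is uncertain, and that stands too. Nothing in the protocol narrows r, and the entry requirement "Stable treatment with NSAIDs or DMARDs in the past 4 months" makes a high r, and so a small gain, possible. If scores are more variable at 3 months than at baseline, the gain can nearly vanish.

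The conservatism depends on balanced allocation within strata. The protocol states no block size, and with unrestricted allocation within strata a simulation put the change test's type I error at 4.9%, 5.3%, 4.9% and 5.4% at r = 0.3, 0.5, 0.7 and 0.9, so the conservatism disappears. Stratified randomisation ordinarily implies restricted allocation, but the type I figures above are conditional on it. The power gain from estimating the slope does not need it.

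Finally, the identity is exact only for the interaction term with both visits observed. The group main effect is a different test that averages in the pre-treatment value. Because the protocol names neither term, this is a further reason to state one contrast.

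**Conclusion.** The concern holds as a matter of efficiency. The change should be made, but the trial is not invalid without it. With equal SDs and an 80% anchor, ANCOVA adds about 13 power points at r = 0.3, 10 at r = 0.5, 6 at r = 0.7 and 2 at r = 0.9. Under the simulated blocked stratification the gain is about 10 points falling to 1. The direction does not depend on equal SDs: apart from a loss of under 0.1 points for the degrees of freedom, ANCOVA on baseline is never less efficient than the change score. The size depends on r and on the SD at 3 months, neither of which the protocol gives, so confidence in the magnitude is moderate. These gains come from baseline ASDAS-CRP. Age and BMI add precision only if they predict outcome given baseline, which the protocol does not show; they belong in the model because they are stratifiers.

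**What to change.** State the primary analysis as ANCOVA: 3-month ASDAS-CRP (or its change, which gives the same group effect once baseline is in the model) on group, with baseline ASDAS-CRP, age and BMI as covariates. Name the adjusted group difference, with its 95% CI, as the single primary contrast, tested at two-sided 0.05. For continuous secondary outcomes where a linear model is suitable, use the same form with each measure's own baseline. That extension is for consistency; no gain was calculated for those outcomes.

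The cost is one or two sentences and about three residual degrees of freedom. No new data are needed, because all three covariates are already required for allocation. The change should be made before any comparison by group is seen, so that the choice of model cannot depend on the results.
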